## 8.2 Notification of the authorities, approval and registration

Before the start of the clinical trial, all necessary documentation will be submitted to the competent supreme federal authority for approval (Bundesinstitut für Arzneimittel und Medizinprdukte, [BfARM]).

The state authorities in each federal state in which the trial will be conducted will also be notified. Prior to start of the study, it will be registered under www.clinicaltrials.gov.

## 8.3 Ethical basis for the clinical trial

The procedures set out in this protocol, pertaining to the conduct, evaluation, and documentation of this study, are designed to ensure that the sponsor and investigator abide by Good Clinical Practice (GCP) guidelines and under the guiding principles detailed in the Declaration of Helsinki. The study will also be carried out in keeping with applicable local law(s) and regulation(s).

Documented approval from appropriate IEC(s)/IRBs will be obtained for all participating centers before start of the study, according to GCP, local laws, regulations and organizations. When necessary, an extension, amendment or renewal of the EC/IRB approval must be obtained. The responsible unit (e.g. EC/IRB, head of the study center/medical institution) must supply to the sponsor, upon request, a list of the EC/IRB members involved in the vote and a statement to confirm that the EC/IRB is organized and operates according to GCP and applicable laws and regulations.

Strict adherence to all specifications laid down in this protocol is required for all aspects of study conduct; the investigator may not modify or alter the procedures described in this protocol.

Modifications to the study protocol will not be implemented by either the sponsor or the investigator without agreement by both parties. However, the investigator or the sponsor may implement a deviation form, or a change of, the protocol to eliminate an immediate hazard to the trial subjects without prior IEC/IRB/sponsor approval/favorable opinion. As soon as possible, the implemented deviation or change, the reasons for it and if appropriate the proposed protocol

amendment should be submitted to the IEC/IRB/head of medical institution/sponsor. Any deviations from the protocol must be explained and documented by the investigator.

All investigators and other staff involved in the study will be informed that the competent federal authorities and authorized representatives of the sponsor have the right to review trial documentation and the trial subjects' medical records at any time.

Details on discontinuation of the entire study or parts thereof can be found in Section 4.10.

## 8.4 Obtaining informed consent from trial subjects

All relevant information on the study will be summarized in an integrated subject information sheet and informed consent form (ICF) provided by the sponsor. A sample subject information and ICF is provided as a document separate to this protocol.

Based on this subject information sheet, the investigator or designee will explain all relevant aspects of the study to each subject prior to her/his entry into the study (i.e. before any examinations and procedures associated with the selection for the study are performed or any study-specific data is recorded on study-specific forms). The investigator will also mention that written approval of the IRB/IEC has been obtained.

Each subject will have ample time and opportunity to ask questions and will be informed about the right to withdraw from the study at any time without any disadvantage and without having to provide reasons for this decision.

Only if the subject voluntarily agrees to sign the informed consent form and has done so, may she/he enter the study. Additionally, the investigator and other information provider (if any) will personally sign and date the form. The ICF will be signed in duplicate, one copy remains with the subject and the second original is to remain in the ISF or, if locally required, in the patient's note/file of the medical institution.

In the event that informed consent is obtained on the date that baseline study procedures are performed, the study record or subject's clinical record must clearly show that informed consent was obtained prior to these procedures.

The ICF and any other written information provided to subjects will be revised whenever important new information becomes available that may be relevant to the subject's consent, or there is an amendment to the protocol that necessitates a change to the content of the subject information and / or the written informed consent form.

The investigator will inform the subject of changes in a timely manner and will ask the subject to confirm her/his participation in the study by signing each revised informed consent form. Any revised written ICF and written information must receive the IEC / IRB's approval / favorable opinion in advance of use.

Part of the monitoring activities are to check that the most recent ICF was used before the trial subject was enrolled and that it was dated and signed by the trial subject himself or herself.

# 8.5 Compensation for health damage of subjects / insurance

All subjects enrolled in this trial are insured in accordance with § 40 AMG article 1 (8) and article 3 under the group insurance contract of GMIHO mbH as a subsidiary company of the sponsor GWT-TUD GmbH with ALLIANZ Versicherungs-AG covering eventually occurring damage caused by the treatment or any actions taken according to the treatment plan. The headquarters, policy number and contact information will be provided in the patient information sheet.

ALLIANZ Versicherungs-AG 10900 Berlin [contact]

Policy Number: AS-9100294133

## 8.6 Confidentiality

All records identifying the subject will be kept confidential and, to the extent permitted by the applicable laws and / or regulations, will not be made publicly available.

Subject names will not be supplied to the sponsor. Only the subject number will be recorded in the eCRF, and if the subject name appears on any other document (e.g. pathologist report), it must be obliterated before a copy of the document is supplied to the sponsor. Study findings stored on a computer will be stored in accordance with local data protection laws. As part of the informed consent process, the subjects will be informed in writing that representatives of the sponsor, IEC / IRB, or regulatory authorities may inspect their medical records to verify the information collected, and that all personal information made available for inspection will be handled in strictest confidence and in accordance with local data protection laws.

If the results of the study are published, the subject's identity will remain confidential. The investigator will maintain a list to enable subjects to be identified in the ISF.

## 9 Statistical methods and sample size calculation

## 9.1 General statistical considerations

### 9.1.1 Description of trial subject groups

Patients with type 2 diabetes duration between 2 and 20 years in the age range from 40 – 75 years showing increased hsCRP (> 2 mg/l but < 10 mg/l) and/or increased PAI 1 (> 15 ng/ml) as well as documented atherosclerotic CVD will be included in this prospective, comparative active controlled, randomized, 2 parallel arms, open study. No further subgroup analyses were intended.

### 9.1.2 Trial populations

For the analysis, patients not fulfilling the selection criteria of the trial ("non-eligible") will be excluded from the statistical analysis. Only casuistic reports will be provided for this group. All other patients will primarily be evaluated in an intent-to-treat analysis (ITT) (full analysis set, FAS). Analyses of efficacy endpoints will be performed on the per protocol analysis set (PPS) defined as the subset of subjects of the FAS who have complete data of primary and secondary target variables at the first (V1) and last visit (V6), and who have no major protocol deviations thought to impact on the efficacy conclusions of the trial.

All patients having received at least one application of study medication are generally evaluable for safety and will be included in the safety analysis set (SAS).

### 9.1.3 Primary target variable

The primary target variable of this study is the change of maximal postischemic forearm blood flow during reactive hyperaemia after 5 min of forearm ischemia (FBF max. ml/100ml) at week 20 and the difference of PWV between treatment groups at EOT.

### 9.1.4 Secondary variables

The secondary variables are the change of AUC of forearm blood flow compared to baseline, the maximal postischemic skin blood flow during reactive hyperaemia after 5 min of forearm ischemia, change of postischemic skin blood flow, pulse wave velocity and laboratory parameters.

### 9.1.5 Interim analysis

An interim analysis is not planned due to the explorative character of the trial.

## 9.1.6 Missing values and outliers

Missing values will not be imputed. Outliers will be identified by data management and have to be checked by the study physician. According to the decision of data management and study physician, outliers will be kept in the database or set to "missing" or "not available".

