## 5.10 Blinding

Not applicable, open-label study.

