## HO: $\Delta$ FBFRiva $\leq \Delta$ FBFASS H1: $\Delta$ FBFRiva $> \Delta$ FBFASS

- Type I error:  $\alpha$  = 0.05, one-tailed t-test for independent samples
- Power: 1-ß = 0.90
- Estimated dropout rate : 25 %
- Minimum of expected clinical relevant difference between the groups in changes of maximal forearm blood flow ( $\Delta$ FBF) = 1.2 ml/100ml with an estimated standard deviation (SD) of  $\sigma$  = 2.4 ml/100ml [Pistrosch, F. et al. Diabetes Care 27: 484-490, 2004]

Sample size should be N = 188 Patients ( $N_{1/2}$  = 94 patients per arm) for a valid number of 141 patients for per protocol analysis. This sample size may also provide enough power for further analyses.

Additionally, the second primary variable is difference of PWV between treatment groups at EOT Extension (after 52 week of treatment). The sample size calculation is based on the following assumptions:

H0: PWVRiva=PWVASS

H1: PWVRiva≠PWVASS

- Type I error:  $\alpha$  = 0.05, t-test for independent samples

- Power: 1-ß = 0.80
- Estimated dropout rate : 20 %
- Minimum of expected clinical relevant difference between the groups in PWV = 0.7 m/s with an estimated standard deviation (SD) of  $\sigma$  = 1.0 m/s

Sample size should be N=80 patients (40 patients per arm) for a valid number of 66 patients for per protocol analysis.

In summary the necessary sample size would be N=188 patients for the study up to week 20 including 80 patients for the extension up to week 52.

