## 9.2 Statistical methods

Descriptive or summary statistics will be displayed for continuous data and for categorical data. All continuous variables will be summarised using the following statistics: n (non-missing sample size), mean, 95 % confidence interval, standard deviation, median, maximum and minimum. The frequency and percentages (based on the non-missing sample size) of observed levels will be reported for all categorical measures. In general, all data will be listed, sorted by subject and visit number. All summary tables will be annotated with the total population size relevant to that table/treatment, including any missing observations.

Comparisons will be tested at the 2-sided 5% significance level. For the primary study endpoint, a one-sided significance level of 5% will be assumed.

T-tests for independent samples will be used for single comparisons between treatment arms (like the primary study endpoint). Analyses of the continuous variables over time will be performed as paired t-Test, repeated measures analysis of variance or mixed models. All analyses of categorical measures will be performed using Fisher's exact test, McNemar's Test or  $\chi^2$  test. Previous correlation analyses of outcome variables and possible predictors will provide evidence for inclusion in analysis. In this trial, most relevant time points for analyses of longitudinal data for secondary study endpoints are at baseline (V1) and after end of treatment (V6).

Individual listings of treatment-emergent adverse events will be provided. The incidence of treatment-emergent adverse events, respectively, will be summarized using WHO SOC terms. Analysis of adverse events will be based on the safety analysis set.

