#### 3.3 Per-Protocol Set (PPS)

Analyses of efficacy endpoints will be performed on the per protocol analysis set (PPS) defined as the subset of subjects of the FAS who have provided complete data of the target variable of interest at the first (V1) and last visit (V6/V13) and who have no major protocol deviations thought to impact the efficacy conclusions of the trial. The classification of protocol violation as major and minor will be done in a data review meeting that will take place after the database is clean.

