#### 6.3 Hypothesis Testing

Unless otherwise specified all hypotheses will be tested at a 5% level of significance against two-sided alternative hypotheses.

Continuous variables will be analyzed by the following test procedures:

First of all the assumption of normally distributed data will be checked with Shapiro-Wilk test by treatment group. If the hypothesis of normally distributed data cannot be rejected for both treatment groups treatments will be compared by an ANCOVA procedure which includes "treatment" as the main factor and "baseline value" as covariate. T-Tests for independent samples will be used to compare groups at baseline.

In the event that the normality assumption is not warranted, data will be log-transformed and normality assumption of the transformed data will be checked by Shapiro-Wilk test. In case of non-rejection of the hypothesis of normally distributed data for both treatment groups, ANCOVA procedure and t-tests as described above will be performed on the basis of log-transformed data.

Point estimates and 95% CI of the difference in (adjusted) mean change from baseline will be provided if data are evaluated on basis of an ANCOVA procedure.

Otherwise Mann-Whitney's-U test on the basis of original data will be applied for comparison of groups at baseline. Mann-Whitney's-U test on the basis of intra-individual differences to baseline will be applied for treatment comparison per visits after baseline. Wilcoxon's signed rank test will be applied to evaluate changes from baseline per treatment group.

Categorical variables with 2 categories will be analyzed using Fisher's exact test (with Yates correction) to compare proportions between treatment groups. Variables with more than 2 categories will be compared by Pearson's Chi-square test. Additionally for each category, the proportions of treatment groups are compared using an (asymptotic) z test. Significant differences in proportions will be flagged, p-values for the z-test will not be shown.

Missing values will not be imputed.

If necessary, modifications of this general procedure will be described in the following sections of chapter 6.

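### Protocol 9.1.6 lets outliers be set to missing by judgement, without a shown measurement error, masking to arm or an all-values analysis, in an open-label trial

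*Protocol*

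**What the plan says.** - **Outliers.** Under Protocol 9.1.6, data management identifies outliers and the study physician checks them. Then: "According to the decision of data management and study physician, outliers will be kept in the database or set to" missing or not available. The section gives no threshold, no requirement of a technical cause, no masking and no comparison analysis. The SAP does not mention outliers, so this rule stands.
- **Consequence.** SAP 6.3: "Missing values will not be imputed". Protocol 9.1.6 says the same. SAP 3.3 also requires complete V1 and V6/V13 data on the target variable for the per-protocol set (PPS).
- **Knowledge of arm.** Protocol 5.10: "Not applicable, open-label study". The sponsor does data management (Protocol 3.4) and runs the central randomisation at its own site (Protocol 5.8).
- **Violations.** SAP 3.3: "The classification of protocol violation as major and minor will be done in a data review meeting", held once the database is clean. Neither attendance nor masking is stated.
- **Masking elsewhere.** SAP section 1 promises blinded review, but only for revisions of the SAP itself.

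**The concern.** Under this rule a genuine measurement can leave the analysis on a judgement, and the people making that judgement may know the arm. If the choice depends on arm, even unintentionally, the groups being compared are no longer the randomised groups with all their observed data, and the nominal 5% level is not guaranteed. Extreme values matter most here, because each has the largest pull on a mean and is also the most likely to be queried. The primary FBF test is one-sided, so a shift in one direction goes straight into the rejection rate. With no all-values analysis planned, a reader of the report could not tell whether the result depends on the removals.

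**Working it through.** **1. Reproduce the plan's sample size.** Inputs from Protocol 9.1.8 and 9.2: "For the primary study endpoint, a one-sided significance level of 5% will be assumed"; "Power: 1-ß = 0.90"; a difference of "1.2 ml/100ml with an estimated standard deviation (SD) of" 2.4 ml/100ml; "Estimated dropout rate : 25"%.

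n per arm = 2 × (1.645 + 1.282)² × (2.4/1.2)² = 68.5, so 69. With the t distribution it is 70. Then 70/0.75 = 93.3, so 94 per arm and 188 in total; 188 × 0.75 = 141. The plan's figures reproduce. About 70 evaluable patients per arm is used below.

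**2. Worst case by hand.** Assume no true effect and normal data. Remove the lowest rivaroxaban value and the highest aspirin value.

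- The expected extreme of 70 normal values is 2.38 SD from the mean. Removing it moves that arm's mean by 2.38/69 = 0.0345 SD.
- Both arms: 0.069 SD × 2.4 = 0.166 ml/100ml, which is 14% of the 1.2 target.
- The residual SD also shrinks. The expected square of the extreme is about 5.85, so the sum of squares per arm falls from 69 to about 63.1, and √(63.1/68) = 0.963. The SD becomes about 2.31.
- Critical difference: 1.656 × 2.31 × √(2/69) = 0.65. Subtracting the shift leaves 0.65 − 0.166 ≈ 0.486.
- The true standard error is about 2.4 × √(2/70) = 0.406, so z ≈ 0.486/0.406 ≈ 1.20 and the tail probability is about 11.6%.

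**3. Simulated null trials** (400,000 per t-test scenario, 20,000 per ANCOVA scenario, 60,000 for the single-reading case; FBF at one-sided 5%, 70 per arm unless stated).

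| What is removed, knowing the arm and favouring rivaroxaban | Type I error |
|---|---|
| Nothing | 5.0% |
| One patient value per arm | 11.7% |
| Same, 94 per arm | 10.8% |
| Same, ANCOVA with baseline, assumed correlation 0.3–0.7 | 9.3–11.2% |
| Same, t with 5 df / log-normal data | 13.6% / 12.2% |
| One patient value in one arm only | 7.8% |
| Two patient values per arm | 21.0% |
| Only unfavourable values beyond 2.5 SD / 3 SD | about 7.5% / 5.6% |
| One of a patient's 8 readings per arm, analysed by patient means, assumed AR(1) correlation 0.5–0.8 | 6.2–5.5% |

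For pulse wave velocity (PWV) at two-sided 5%, one patient value per arm gives 9.7% at 33 per arm and 9.2% at 40 per arm.

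**4. After masking.** A fixed rule applied without regard to arm (pooled |z| above 3 or 3.5) gives 5.0%. The inflation comes from choice that depends on arm, not from removing outliers as such.

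**The case against.** **The headline scenario is harsher than the rule.** Protocol 9.1.6 covers outliers only, whereas the 11.7% always deletes the extreme value. Among 70 normal values the extreme lies beyond 3 SD in only 1 − 0.99865⁷⁰ = 9% of arms, and beyond 2.5 SD in 1 − 0.99379⁷⁰ = 35%. A reader might infer that the rule doubles the type I error. The documents do not support that: it takes removal in both arms, chosen by arm and in one direction, of values that ordinary screening would often not flag. This stands, and it is why the lower rows of the table belong beside the headline figure.

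**A removed reading need not remove the patient.** A reader might infer that any value set to missing costs the patient their place in the primary analysis. SAP 4.8.1 builds ΔFBF from 5 baseline and 8 post-ischaemic readings, and SAP 6.11.1 analyses repeated measurements with an AR(1) structure, so one lost reading leaves the patient in. This also stands. The protocol still defines the primary variable as maximal flow (Protocol 6.1.1), where losing the peak reading changes the patient's value directly.

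**Controls exist.** Protocol 7.2 requires written clarification of implausible values, an audit trail, role-based access, and locking before export. Two parties act on each outlier. Removed values can therefore be traced and recovered, and describing them as destroyed would be wrong. These controls record a choice that depends on arm but do not prevent it.

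**Knowledge of arm is possible, not shown.** Allocation is issued by the sponsor's medical consulting department (Protocol 5.8), which is not named as data management. No text says that outliers are reviewed by arm. Equally, no text says that they are reviewed without it.

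**Violations.** A reader might extend the inflation figures to the classification of violations. That classification defines the PPS, while Protocol 9.1.2 and SAP 3.1 evaluate patients primarily by ITT/FAS. Nothing calculated here measures it, and what the meeting will see is not stated.

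**Conclusion.** The concern holds as a weakness in a stated rule. Protocol 9.1.6 permits removal by judgement with no technical criterion, no masking and no all-values analysis, and the SAP adds nothing.

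The worst case for FBF is about 12% instead of 5%, or about 9–11% with baseline ANCOVA, with a shift of about 0.17 ml/100ml. It assumes no true effect, roughly normal data, about 70 patients per arm, and one whole-patient value per arm removed with the arm known and in rivaroxaban's favour. Under milder assumptions the error is about 5.5–7.5%. The range describes how sensitive the test is; nothing in the documents indicates that anyone would use the rule this way. The classification of violations is a secondary point that affects the PPS only.

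**What to change.** Change Protocol 9.1.6 and add a matching SAP section:

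1. A value is set to missing only for a documented technical error, for example a cuff or strain-gauge failure. All other outliers stay in.
2. The decision is made and signed off from listings without treatment arm, before database lock.
3. The primary analysis is reported with and without the removed values.

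Secondary change, to SAP 3.3: classify major violations from listings that show neither arm nor post-baseline FBF or PWV values.

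Cost: wording, arm-free listings and one repeated analysis, so a little extra data-management and statistical work. Visits, sample size and clinical procedures do not change. Label: cheap improvement.

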### 9.1.7 Reporting conventions

P-values ≥ 0.001 will be reported to 3 decimal places; p-values less than 0.001 will be reported as "< 0.001". The mean, standard deviation, and any other statistics other than quantiles, will be reported to one decimal place greater than the original data. Quantiles, such as median, or minimum and maximum will use the same number of decimal places as the original data. Estimated parameters, not on the same scale as raw observations (e.g. regression coefficients) will be reported to 3 significant digits.

### 9.1.8 Sample size calculation

The primary variable is change of forearm blood blow with venous occlusion plethysmography( $\Delta$ FBF) after forearm ischemia after 20 weeks treatment. The sample size calculation is based on the following assumptions:

